5.1.1.1.2 End date of the Dosing Period

Dosing Periods are specified in section of study periods.

5.1.1.1.3 Study periods

The total duration of the study for an individual study participant is 17 days to 48 days and will include:

- A Screening Period (2 to 28 days before IMP administration)
- Two Dosing Periods (4 days each, with IMP administration on Day 1 of each Dosing Period)
- A Wash-out Period following Dosing Period 1 (7 to 10 days between the 2 IMP administrations)
- An SFU Visit/Withdrawal Visit (7 to 9 days after the last IMP administration)

Table 5-1: Duration of Each Period

Period	Duration
Screening Period	Prior to the date of first IMP administration (Relative Day -28 to -2)
Dosing Period 1	Defined as Relative Day -1 to 3
Wash-out Period	Defined as Relative Day +3 to +6 (~ + 9)
Dosing Period 2	Defined as Relative Day -1 to 3
Safety Follow-Up Period	Defined as Relative Day +3 to +6 (~ + 8)

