5.1.1 General study level definitions

5.1.1.1 Analysis Time Points

5.1.1.1.1 Relative day

Relative day will be derived with the date of IMP administration in each Dosing Period as reference for that specific Dosing Period.

For days on the day of IMP administration in each Dosing Period

Relative day will be calculated as follows:

Relative day = Current date - Date of IMP administration + 1
i.e., the day of IMP administration in each Dosing Period will have a relative day of '1'.

For days prior to IMP administration in each Dosing Period

Relative day will be prefixed with '-' and calculated as follows:

Relative day = Current date - Date of IMP administration within the same Dosing Period
e.g., the day prior to the IMP administration will have a relative day of '-1'.

For days prior to the first IMP administration in the Screening Period

Relative day will be prefixed with '-' and calculated as follows:

Relative day = Current date - Date of first IMP administration
e.g., Screening Visit that is 7 days prior to the first IMP administration will have a relative day of '-7'.

For days after the day of IMP administration in Dosing Period

Relative day will be prefixed with '+' and will be calculated as follows:

Relative day = Current date - Date of IMP administration within the same Dosing Period
e.g., the day after IMP administration in a Dosing Period will have a relative day of '+1'.

For days after the Dosing Period

Relative day will be prefixed with '+' and calculated as follows:

Relative day = Current date - Date of last IMP administration
e.g., A certain day in a washout period following Dosing Period 1 that is 7 days after IMP administration in Dosing Period 1 will have a relative day of '+7'.
e.g., Safety Follow-Up Visit that is 8 days after the last IMP administration will have a relative day of '+8'.

Relative day will not be calculated for partial dates. Relative day for partial days will be displayed as '--' to distinguish it from missing values which are displayed as blanks.

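### Does SAP Table 5-1 leave Safety Follow-Up visits outside every study period and put some days in two periods?

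*SAP*

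**What the plan says.** SAP section 5.1.1.1.1 counts days after dosing without adding one: "the day after IMP administration in a Dosing Period will have a relative day of" +1. For follow-up, "Safety Follow-Up Visit that is 8 days after the last IMP administration will have a relative day of '+8". The day before dosing is -1, and each Dosing Period is counted from its own dose.

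Section 5.1.1.1.2 sets no end date of its own: "Dosing Periods are specified in section of study periods". Section 5.1.1.1.3 then gives two things.

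- A bulleted list, with "A Wash-out Period following Dosing Period 1 (7 to 10 days between the 2 IMP administrations" and "An SFU Visit/Withdrawal Visit (7 to 9 days after the last IMP administration" (closing brackets omitted), Dosing Periods of 4 days, and a total of 17 to 48 days per participant.
- Table 5-1, in which each Dosing Period runs from -1 to 3, Wash-out is "Defined as Relative Day +3 to +6 (~ + 9", and Safety Follow-Up is "Defined as Relative Day +3 to +6 (~ + 8".

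The bracketed tilde is not explained. Footnote b to SAP Figure 1-1 places each Dosing Period on Day -1 to Day 3, with discharge about 48 hours after dosing.

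**The concern.** On the SAP's own day count, SFU visits fall on +7, +8 or +9, yet the Safety Follow-Up Period stops at +6, or at most +8. Wash-out runs to +6 through +9, which are the calendar days of Period 2 check-in when doses are 7 to 10 days apart, and Table 5-1 also starts Dosing Period 2 on that day. Finally, the Dosing Periods end at 3 and the next period starts at +3, although the 48-hour day is +2 on the relative-day scale.

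If programs assigned records to periods from this table, follow-up laboratory, ECG and vital-sign values for all 24 planned participants could belong to no period, and Period 2 check-in records could belong to two. Table 5-2 names the Wash-out Period when it says where a replacement Period 2 baseline may come from, so baselines might also seem exposed.

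**Working it through.** **Inputs (SAP 5.1.1.1.1 and 5.1.1.1.3).** Screening starts 2 to 28 days before dose 1, the doses are 7 to 10 days apart, and the SFU visit is 7 to 9 days after the last dose. Days after a dose are counted as current date minus dose date.

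**The plan's own total.** Duration = screening days + dose interval + days to SFU + 1.

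- Shortest: 2 + 7 + 7 + 1 = 17.
- Longest: 28 + 10 + 9 + 1 = 48.

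Both match the stated 17 to 48 days.

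**Table 5-1 period lengths**, in the order Screening, Dosing 1, Wash-out, Dosing 2, Follow-Up, with the follow-up bound paired to the visit day (+6 for a visit on +7, +8 for a visit on +9):

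- 3 read as nominal Day 3 (= +2): 1 + 4 + 4 + 4 + 4 = 17 and 27 + 4 + 7 + 4 + 6 = 48.
- 3 read as relative day +3: 1 + 5 + 4 + 5 + 4 = 19 and 27 + 5 + 7 + 5 + 6 = 50.

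The first reading matches the stated 4-day Dosing Periods. Its agreement with 17 to 48 does not validate the table. By calendar date, Period 2 Day -1 is counted twice and the SFU visit day not at all, and the two errors cancel.

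**SFU visit.** There are 4 dose intervals × 3 visit days = 12 combinations.

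| Reading of the upper bound | Visits outside the period | Combinations |
|---|---|---|
| Moves with the visit day (visit day minus 1) | +7, +8, +9 | 12 of 12 |
| Common ceiling of +8 | +9 only | 4 of 12 |

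**Period 2 check-in.** Counted from dose 1, Day -1 is interval minus 1: 7 - 1 = +6, up to 10 - 1 = +9. That equals the end of Wash-out in all 12 combinations. Counted from its own dose, as section 5.1.1.1.1 provides for days before dosing within a Dosing Period, the day is labelled -1 and matches Dosing Period 2 only.

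**Day 3.** The 48-hour day is dose date + 2, so +2. If 3 means nominal Day 3, the Dosing Period abuts the next period at +3. If it means +3, that day falls in two periods.

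**Where the periods could affect an output.**

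- *Replacement baselines (Table 5-2).* For Period 2 the search covers Wash-out together with predose Dosing Period 2. Moving Day -1 from one to the other leaves that combined window unchanged.
- *Day -1 data.* The Schedule of Activities (SAP Table 1-2) has no vital signs, ECG or laboratory tests on Day -1. Physical examination is done then but only listed (10.3.4).
- *SFU data.* The SFU is visit V4 in the schedule. Laboratory, vital-sign and ECG values are summarised at scheduled time points (10.3.1.1, 10.3.2.1, 10.3.3.1), and withdrawal assessments are also considered for that visit (5.1.1.1.4).
- *Adverse events and concomitant medications.* Sections 10.2 and 6.3 assign them from one dose to the next, with no end after dose 2. Table 5-1 is not used.
- *Primary analysis.* PK parameters use actual sampling times (9.2.1), and the period term in the model (9.3.2) is the dosing occasion.

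**The case for a change.** The best case for amending the table is that it is wrong on its face and cheap to correct. Section 5.1.1.1.2 relies on this section for Dosing Period ends, and relative day appears in the medication, adverse event and laboratory listings. A Period 2 check-in record could be shown as -1 under the rule for days before dosing, or as +6 to +9 under the rule for days after a Dosing Period. One consistent set of bounds exists: Dosing Periods -1 to +2, Wash-out +3 to +5 (up to +8), Safety Follow-Up +3 to +7 (up to +9). It leaves no gap or overlap in any of the 12 combinations, and the lengths sum to 1 + 4 + 3 + 4 + 5 = 17 and 27 + 4 + 6 + 4 + 7 = 48.

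The inconsistency stands, and so does the possible label ambiguity. The wider claims do not. Saying that all 24 participants' visits are excluded assumes that the undefined tilde makes the bound follow the visit day. Double assignment of Day -1 requires counting from dose 1 a day that the SAP labels from dose 2. Figure 1-1 footnote b also settles the extent of the Dosing Periods without Table 5-1. Above all, no summary or analysis selects records by the faulty bounds.

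**Conclusion.** Table 5-1 contains a clerical slip, and no change to the plan is needed. An SFU visit on +9 is outside the tabulated period however the table is read. Visits on +7 and +8 are outside only if the bound is paired with the visit day. The overlaps depend on counting Period 2 check-in from dose 1 and on reading 3 as +3.

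The effect is confined to period or relative-day labels in by-participant listings. No baseline, safety summary, treatment assignment of an adverse event or medication, PK parameter or 90% confidence interval changes.

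This rests on two assumptions: that programmers follow the SAP's visit-based summaries and dose-to-dose rules as written, and that they label Period 2 Day -1 from its own dose. Both are what the SAP's text directs. The bulleted visit windows, the worked +8 example and the 4-day Dosing Periods give an analyst enough to set sensible labels.

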5.1.1.1.4 Mapping of assessments performed at Withdrawal Visit

Safety assessments made at a withdrawal visit that correspond to a scheduled visit will be summarized at the scheduled visit to corresponding to the withdrawal visit if the assessment was scheduled to occur at that visit. Such assessments at the withdrawal visit will also be considered for safety follow up/ withdrawal visit.

5.1.1.1.5 Definition of Baseline values

Baseline will be the last available predose result for each Dosing Period. Each Dosing Period will therefore have its own Baseline, independent of the other Treatment Periods unless the data collection is not scheduled (e.g., clinical laboratory tests). If no predose results are available for Dosing Period 1, then the Screening result will be used as the Baseline result for that Dosing Period.

Table 5-2: Definition of Baseline

Measurement	Definition of Baseline
Vital Signs	Day 1, Pre-dose value in each period. If this value is unavailable, the latest available value before dosing will be imputed. For Dosing Period 1, the latest value in Screening Period and Dosing Period 1 before dosing can be used.

Measurement	Definition of Baseline
	For Dosing Period 2, the latest value in Wash-out Period and Dosing Period 2 before dosing can be used.
12-lead ECG	Day 1, Pre-dose value in each period. If this value is unavailable, the latest available value before dosing will be imputed. For Dosing Period 1, the latest value in Screening Period and Dosing Period 1 before dosing can be used. For Dosing Period 2, the latest value in Wash-out Period and Dosing Period 2 before dosing can be used.
Clinical laboratory tests (hematology, clinical chemistry, and urinalysis)	The Screening value for each period. If this value is unavailable, unscheduled visit closest to and before dosing of the Dosing Period 1 will be imputed for both Dosing Period. For Dosing Period 2, the latest value in Wash-out Period and Dosing Period 2 before dosing can be used if any other baseline value is unavailable.

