8.2.3 Electrocardiograms

Single 12-lead ECG (except at predose on Day 1 of each Dosing Period, when 3 Baseline values will be measured at 2- to 5-minute intervals) will be obtained as outlined in the Schedule of Activities (see [Table 1-1](#)) using an ECG machine that automatically calculates the heart rate and measures PR, QRS, QT intervals, and QT interval corrected (QTc).

All ECG recordings should be taken with the study participant resting in the supine position for at least 10 minutes before the recording.

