^g 12-lead ECGs are recorded at Screening, at predose, 1, 4, 8, 24, and 48 hours postdose, and at the SFU Visit/Withdrawal Visit. At predose on Day 1 of each Dosing Period, 3 Baselines values will be measured at 2- to 5-minute intervals.

^h IMP administration: BRV 50mg will be administered as a 50mg tablet (Treatment A [reference]) or as dry syrup (1.25g of BRV granules for oral solution 4% w/w; Treatment B [test]) under fasting conditions.

ⁱ Blood samples for PK analysis are collected at predose, and 0.25, 0.5, 0.75, 1.0, 1.25, 1.5, 2, 3, 4, 6, 8, 12, 16, 24, 36, and 48 hours postdose. Allowable deviations from these scheduled PK sampling times are provided in Table 8-2 of the protocol.

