Derived variables in general will display the mean, SD and median to 1 more decimal place than the variables used in the derivation. If the number of decimal places reported in the raw data is varied then use either the maximum raw number of reported decimal places or 3, whichever is the lowest, as a guide for the descriptive statistics.

If participants have more than one observation for a given time point, the observation closest to the intended time point will be used. If both observations are equidistant from the intended time point, then the later value will be used.

Refer to Appendix 3 (Section 11.3.1 and Section 11.3.2) for standard reporting procedures of PK concentrations and parameters in listings, tables, and figures.

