10.3.3 Electrocardiograms

The following twelve-lead ECG variables will be obtained: heart rate, PR, QRS, QT intervals, and QTcF.

For the results measured in triplicate, the averaged value at each time point will be used for by-visit summaries.

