10.3.3.1 Electrocardiogram Values Over Time

Twelve-lead ECG variables and changes from Baseline will be summarized using descriptive statistics by treatment (tablet or dry syrup) at each scheduled time point.

The following cut-points in QTcF (raw data and change from Baseline) will be summarized categorically by treatment (tablet or dry syrup) (number and percentage of participants) and timepoint.

Raw QTcF data:

- <450msec
- $\geq 450\text{msec}$ to $<480\text{msec}$
- $\geq 480\text{msec}$ to $<500\text{msec}$
- $\geq 500\text{msec}$

Change from Baseline QTcF:

- <30msec
- $\geq 30\text{msec}$ to $<60\text{msec}$
- $\geq 60\text{msec}$

Electrocardiogram findings will be listed for the RS.

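### Do the SAP's Baseline rules waste the triplicate predose ECGs and the Period 1 Day 3 laboratory results?

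*SAP*

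**What the plan says.** **ECG.** Protocol 8.2.3 takes single ECGs except before the Day 1 dose of each period, "when 3 Baseline values will be measured at 2- to 5-minute intervals". SAP Table 1-2, footnote g, agrees: "At predose on Day 1 of each Dosing Period, 3 Baselines values will be measured at 2- to 5-minute intervals". Four SAP statements bear on how those readings become a Baseline:

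- 5.1.1.1.5, lead sentence: "Baseline will be the last available predose result for each Dosing Period".
- Table 5-2, ECG row: "Day 1, Pre-dose value in each period".
- 5.1, general rule for repeated observations: "If participants have more than one observation for a given time point, the observation closest to the intended time point will be used". If two are equally close, the later one is taken.
- 10.3.3, ECG-specific rule: "For the results measured in triplicate, the averaged value at each time point will be used for by-visit summaries".

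SAP 10.3.3.1 then says: "Twelve-lead ECG variables and changes from Baseline will be summarized using descriptive statistics by treatment (tablet or dry syrup) at each scheduled time point". It adds QTcF categories, including increases of at least 30 and at least 60 msec, by treatment and time point.

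**Laboratory.** Table 5-2 sets the Baseline as "The Screening value for each period". The text before the table says each period has its own Baseline except where collection is not scheduled, and gives clinical laboratory tests as the example. Table 1-2 schedules laboratory tests at Screening, on Day 3 of each Dosing Period and at Safety Follow-Up, with none on Day -1 or Day 1.

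**The concern.** Read literally, the section that defines Baseline never mentions averaging. A programmer who worked only from its lead sentence, or from the general rule in SAP 5.1, could take one of the three predose ECGs. The averaging sentence in 10.3.3 speaks of by-visit summaries and does not name Baseline. A single-reading Baseline would make every change from Baseline noisier and would produce more chance entries in the QTcF increase categories.

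For laboratory tests, the Period 2 change by formulation is measured from before Period 1. It therefore contains whatever happened in Period 1, including exposure to the other formulation and the Period 1 blood draws. A shift that began under one formulation and persisted would be tabulated under both. A more recent result, from Period 1 Day 3, exists and is not used as Baseline. Laboratory changes and ECG parameters are both stated safety endpoints in SAP Table 1-1.

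**Working it through.** **1. Which rule governs the three ECGs.** Scheduled ECGs are single everywhere except before the dose on Day 1. The averaging rule in SAP 10.3.3 therefore has no scheduled use other than the Baseline readings. The change and QTcF-category outputs in 10.3.3.1 are summaries by time point, so they fall within its wording. The ECG row of Table 5-2 says neither last nor which replicate. The lead sentence of 5.1.1.1.5 and the repeat-observation rule of 5.1 are general, and a rule specific to ECGs would ordinarily take precedence. Averaging is the reading under which all the provisions have a purpose.

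**2. What a single reading would cost.** Let each reading have error SD s, with correlation r among the three predose readings and a post-dose error independent of them.

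- SD of change, single Baseline: s × √2.
- SD of change, mean of three: s × √(1 + (1 + 2r)/3).
- With r = 0: √2 / √(4/3) = 1.225, so the single-reading SD is 22% larger. Equivalently, averaging cuts the SD by 18%.
- With r = 0.3, 0.5 and 0.8, averaging cuts it by 12%, 9% and 3%.

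Post-dose ECGs are at 1, 4, 8, 24 and 48 hours, so 24 participants × 2 periods × 5 = 240. The expected number of chance increases of at least 30 msec is 240 × P(Z > 30 / SD of change). The documents give no reading SD, so s is an assumption, and r = 0 throughout:

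| Assumed s (msec) | Single Baseline | Mean of three |
|---|---|---|
| 6 | 0.05 | 0.002 |
| 8 | 0.96 | 0.14 |
| 10 | 4.1 | 1.1 |

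The count depends mainly on the assumed s. It also measures a rule that the SAP does not clearly adopt.

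**3. Laboratory timing.** The visit windows first reproduce the stated study duration: 2 + 7 + 7 + 1 = 17 days and 28 + 10 + 9 + 1 = 48 days. From the same windows:

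- Screening to Period 2 dose: 2 + 7 = 9 to 28 + 10 = 38 days.
- Period 1 Day 3 to Period 2 dose: 7 − 2 = 5 to 10 − 2 = 8 days.
- Drug left at Day 3, with the 9 h half-life in Protocol section 2: 2^(−48/9) = 2.5%.

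Day 3 is more recent, but it is the post-dose assessment of Period 1 (SAP Table 5-1 places it in that period).

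**4. What each laboratory Baseline does to the comparison.** With a common Screening value Y0, the within-participant contrast is (Y_B − Y0) − (Y_A − Y0) = Y_B − Y_A, so Baseline cancels for anyone who completes both periods.

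Now use Period 1 Day 3 as the Period 2 Baseline. Assume 12 participants per sequence, and an effect of each formulation that is present at its own Day 3 and gone before the next dose.

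- True shift +1 on both: Period 1 changes are +1 and Period 2 changes are 0. Each formulation shows (1 + 0)/2 = +0.50. Screening shows +1.00 and +1.00.
- True shift +1 tablet, +2 dry syrup: tablet shows (1 + (1 − 2))/2 = 0.00, and dry syrup shows ((2 − 1) + 2)/2 = 1.50. Screening shows 1.00 and 2.00.
- In that second case, simulated with an assumed within-participant SD of 0.5, the SD of the formulation difference is 0.253 with Day 3 and 0.145 with Screening.

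**5. The cost of Screening.** One participant with a shift that lasts from Period 1 into Period 2 adds 1/24 = 4.2 points to each formulation column. PK blood drawn since Screening is 17 × 4 = 68 mL by Period 1 Day 3 and 34 × 4 = 136 mL by Period 2 Day 3. Each formulation is given in each period, so with balanced sequences this falls on both.

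**The case for a change.** The strongest case on the ECG side is that no sentence says outright that the averaged value is the Baseline, while two general rules can be read as selecting one reading. That is true: the wording is incomplete. It shows an ambiguity, not a decision to discard data, and the ECG-specific rule resolves it in the sensible direction.

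On the laboratory side, the case is that adverse events are assigned to one formulation by onset (SAP 10.2), whereas a persisting laboratory shift is counted under both and the table hides where it began. For a shift that truly persists, a Day 3 Baseline would remove that double count. This stands as a limitation. But the same Baseline misstates effects that resolve between Day 3 and the next dose, as step 4 shows, so neither choice is better in every case.

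A milder alternative keeps Screening and shows changes by period within formulation. It does no harm, but it only re-displays what SAP 10.3.1 already lists by sequence, participant and period or visit, with change from Baseline and range flags. A persisting shift can be traced there.

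The charge that Screening contradicts the section's own lead rule fails, because the next sentence of 5.1.1.1.5 makes laboratory tests the exception.

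**Conclusion.** No change follows. The ECG point is a missing detail that analysts fill by averaging the predose triplicate. Even on the unfavourable reading, the loss is at most a 22% larger SD of change under independent errors, and less if readings taken 2 to 5 minutes apart correlate. The chance-outlier counts rest on reading SDs that are not in the documents.

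The laboratory point is a fair trade-off, stated openly in the SAP. A common untreated Baseline is exchanged for one that lies 9 to 38 days before the Period 2 dose and lets lasting Period 1 effects into Period 2 changes. The formulation contrast is protected because Baseline cancels for participants who complete both periods, and the listings show individual histories. The illustration of the alternative rests on assumed effect sizes, an assumed SD and balanced sequences.

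Both points concern descriptive outputs for the other safety endpoints. The Cmax and AUC(0-t) analysis and the sample size do not depend on them.

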5.1.1.2 Protocol Deviations

Important protocol deviations (IPDs) will be summarized by treatment sequence, and overall using the SS and PK-PPS. The summary will include the following:

- Number and percentage of participants with no IPDs
- Number and percentage of participants with at least one IPD
- Number and percentage of participants by type of protocol deviation

By-participant listings of IPDs as identified in the Data Cleaning Meeting and DEM will be provided by treatment sequence, period, treatment (tablet or dry syrup) using the SS. This will include deviation type, deviation description, and whether the deviation led to exclusion from the PK-PPS.

Protocol deviations (e.g., missing assessments or visits) related to COVID-19 will be listed separately.

